Synthetic double stranded RNA (dsRNA) such as poly-IC, which consists of a pair of strands of poly-inosinic and poly-cytidylic acids, are not normally found in mammalian cells, but they are the basic genetic material or are replication byproducts of many viruses (31). Plain Poly-IC itself proved to be ineffective in primates because it is rapidly inactivated by natural enzymes in the blood. However stabilized poly-IC with poly-lysine is a very stable dsRNA that is a potent interferon inducer in man. Early, short term, high dose cancer trials showed that high dose poly-ICLC could induce very large amounts of interferon production in man, but with only modest therapeutic effects and moderate transient toxicity (31). Low dose poly-ICLC is a potent clinical activator of a variety of host defense mechanisms that go well beyond simple induction of interferons and which include reversal or preemption of certain viral or tumor induced inhibitions, broad immune stimulation, gene regulatory and specific antiviral, and anticancer effects, with little or no toxicity (31, 32).

In this study low dose poly-ICLC will be used as a direct immune-enhancer in order to activate T-cells, natural killer cells, and, dendritic cells, release of cytokines such as interferons, interleukins, corticosteroids, and tumor necrosis factor (TNF). Its recently demonstrated effect on dendritic cells through Toll-like receptors (TLR3) may be especially important since CDX-1401 directly targets these cells (33). As described above, dendritic cells play a critical role in the immune response by recognizing pathogens and presenting their antigens to the immune system. The poly-ICLC used

PROTOCOL TITLE: I 49217 - Phase 1 CDX-1401/ Poly-ICLC +Decitabine +Nivolumab in Patients with MDS or Low Blast Count AML

in this study will provide an adjuvant effect for the CDX-1401 with increased antibody and cellular immune response to NY-ESO-1 antigen.

Clinical Studies with CDX-1401 and adjuvants

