11.4 Evaluations Performed on Day 1 of each Cycle

The following evaluations will be performed prior to CDX-1401/poly ICLC dosing or infusion of decitabine on Day 1 of each cycle or prior to premedication, if administered (may be performed up to 3 days prior to day of infusion), unless otherwise indicated:

- Physical examination
- Vital signs (i.e., temperature, heart rate, respiratory rate, oxygen saturation, blood pressure, body weight)
- Hematology: CBC with manual differential (Once per week of each cycle during cycles 1-4, from cycles 5 onward on day 1 and as clinically indicated)
- Hematological Improvement (HI) in MDS or low blast count AML patients treated with the combination in order to provide descriptive characteristics.
 - This will be assessed using results of blood counts on day 1 of each cycle.
- Chemistry: CMP, LDH, uric acid, amylase and, lipase (Once per week each cycle during cycles 1-4, from cycles 5 onward on day 1 and as clinically indicated)
- ECOG performance status

PROTOCOL TITLE: I 49217 - Phase 1 CDX-1401/ Poly-ICLC +Decitabine +Nivolumab in Patients with MDS or Low Blast Count AML

- Correlative blood sampling prior to study drug dosing Once per week each cycle during Cycles 1-4; from Cycle 5 onward once every 2 weeks (see Section 11.11.1)
- Decitabine administration: Day 1-Day 5 of each cycle (per standard of care for patient safety)
- Nivolumab administration: Day 1 and Day 15 of each cycle (+/-7 days)
- Concomitant Medications
- Adverse events

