11.11.7 Dendritic Cell Function

In the event that we do not observe antigen specific immune responses, this could reflect APC dysfunction related either to the underlying malignancy, or to treatment with decitabine. The function of APCs in MDS has not been tested, thus we will determine whether cultured APCs from our enrolled MDS patients are able to effectively process and present antigen in order to activate T-cells. Exposure to decitabine has been previously shown to enhance the development and maturation of APCs in solid tumor models (64), as well as to enhance immune recognition in other hematological malignancies (65). We will examine APC function at baseline and following 2 and 4 cycles of decitabine treatment (3 time points). For these assays, blood samples will be obtained and cultured under conditions known to induce APC differentiation (66, 67). The ability of these cells to activate NY-ESO-1 specific T-cells derived from either autologous peripheral blood mononuclear cells or from ovarian cancer patients with NY-ESO-1 expressing tumors, (depending upon the HLA type of the patient) will be determined by the ELISPOT technique for IFN γ , as above. We will also assess the ability of these cells to induce an allo-reactive T-cell response from

PROTOCOL TITLE: I 49217 - Phase 1 CDX-1401/ Poly-ICLC +Decitabine +Nivolumab in Patients with MDS or Low Blast Count AML

healthy donor T-cells. These assays will test the function of APCs in MDS patients and determine if exposure to decitabine has an effect upon this function.

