The induction of antitumor T-cell responses associated with IFN γ production are believed to be critical to the effects of cancer vaccination in solid tumors, however such responses are limited by the action of immunosuppressive Tregs which allow escape by malignant cells (59, 60, 68). Recently Tregs have been demonstrated to be complex, differentiating and migrating in response to signals from the immune system (60). Specific subsets of Tregs have been demonstrated to have differential suppressive effects upon anti-tumor immune responsiveness (60, 69). One study in MDS and AML patients treated with azacitidine following BMT suggests that HMAs alter Treg function by promoting graft versus leukemia effects over graft versus host effects, while another has demonstrated enhanced immuno-suppressive effects (49, 68). In order to determine if MDS patients undergoing therapy with CDX-1401/poly ICLC decitabine and nivolumab demonstrate changes in Treg differentiation favoring anti-tumor immune responsiveness over immune suppression, we will analyze Tregs sampled serially for changes in the expression of markers (including CD127, CD45RA, CXCR3 and Helios) associated with Treg biological function using flow cytometry (56, 59, 70, 71). Significant changes in Treg subsets with therapy would suggest that decitabine can alter the immune milieu in patients with MDS.

The methods to analyze the T cell response to cancer antigens used in this study are well established. However, as T cell biology and immune regulation are very active fields of discovery, the opportunity exists to refine and extend the analysis of the T cell response. Therefore, although most of the blood drawn for the analysis of the immune response will be used for the assays listed in this section, a small part may be used to explore other aspects of the T cell response using novel techniques such as time of flight cytometry. This work may also involve establishing T cell lines and clones in culture, and collaborations with investigators outside of Roswell Park Cancer Institute. As these exploratory approaches, by definition, have not yet been validated, the results will not be endpoints in the evaluation of the current study.

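### Section 11.11.7 credits changes in APC function and Treg subsets to decitabine, although vaccine, poly-ICLC and nivolumab are given over the same interval and the responder T cells are not fixed

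*Combined protocol and SAP*

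**What the plan says.** Section 11.11.7 (Dendritic Cell Function) gives the reason for the APC assay: "In the event that we do not observe antigen specific immune responses, this could reflect APC dysfunction". Patient APCs are cultured from blood at three time points: baseline, after 2 cycles and after 4 cycles.

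Two readouts are planned. The first is an IFN-gamma ELISPOT, described as "The ability of these cells to activate NY-ESO-1 specific T-cells derived from either autologous peripheral blood mononuclear cells". As an alternative source of responders, the section allows T cells taken from women with ovarian cancer, the choice being made by HLA type. The second readout uses healthy-donor T cells: "We will also assess the ability of these cells to induce an allo-reactive T-cell response from" such donors. The section says the assays will "determine if exposure to decitabine has an effect upon this function".

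The Treg text in the same section sets out to study therapy with the whole combination but closes on one agent: "Significant changes in Treg subsets with therapy would suggest that decitabine can alter the immune milieu in patients with MDS".

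Section 2.3.1 says of poly-ICLC: "Its recently demonstrated effect on dendritic cells through Toll-like receptors (TLR3) may be especially important since CDX-1401 directly targets these cells". Appendix J places baseline within the 4 weeks before the first CDX-1401/poly-ICLC dose. Section 11.4 schedules "Correlative blood sampling prior to study drug dosing Once per week each cycle during Cycles 1-4", so pre-dose blood exists on Cycle 1 Day 1, but 11.11.7 does not list it as an APC time point.

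**The concern.** There are two separate problems.

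**Attribution.** Everything in the regimen starts between baseline and the cycle 2 sample. The protocol itself says that two of the other agents act on dendritic cells. A baseline comparison tests whether anything in the regimen changed the readout. It does not test whether decitabine did. This applies to every responder type and to the Treg analysis.

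**Responder cells.** An ELISPOT count depends on the responder T cells as well as on the APCs. If autologous responders are taken afresh at each visit, the responder pool is expected to grow during treatment, and counts can rise while APC function stays the same. Conversely, a patient with no NY-ESO-1 T cells gives a null autologous readout whether or not the APCs work. That is the patient for whom the protocol offers APC dysfunction as a possible explanation.

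At stake is how a negative immune result is explained, and whether decitabine is credited with effects that may belong to its partners.

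**Working it through.** The plan gives no sample size, power or error rate for this assay, so there is no figure of that kind to reproduce.

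**1. Exposure at each sample.** Inputs are from 10.1: vaccine on Day -14 and on Day 15 of cycles 1-4; nivolumab twice per cycle in cycles 1-4; decitabine on 5 days per cycle. After c completed cycles on schedule (c up to 4), vaccine doses = 1 + c, nivolumab doses = 2c and decitabine days = 5c.

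| Sample | Vaccine doses | Nivolumab doses | Decitabine days |
|---|---|---|---|
| Baseline | 0 | 0 | 0 |
| Cycle 1 Day 1, pre-dose | 1 | 0 | 0 |
| After cycle 2 | 1 + 2 = 3 | 2 × 2 = 4 | 5 × 2 = 10 |
| After cycle 4 | 1 + 4 = 5 | 2 × 4 = 8 | 5 × 4 = 20 |

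The 5 vaccine doses after cycle 4 match the total stated in 10.1. No comparison from baseline changes decitabine alone. Starting from Cycle 1 Day 1 removes the first vaccine from the contrast. It leaves 3 - 1 = 2 or 5 - 1 = 4 further vaccine doses and all of the nivolumab.

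**2. Does the autologous responder pool change?** Table 3 in 2.2 covers 9 patients given vaccine plus decitabine, without nivolumab.
- CD4 response present: 3/9 before, 7/9 after.
- CD8 response present: 0/9 before, 5/9 after.
- Either present: 3/9 before, 8/9 after (5 gained, 0 lost; exact McNemar p = 2 × 0.5^5 = 0.0625).

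So 6/9 had no detectable NY-ESO-1 T cells before treatment, and 1/9 had none afterwards. For such a sample, a null autologous ELISPOT says nothing about the APCs.

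**3. Illustration of the responder effect.** The model is readout = APC function × responder strength × noise + small background.
- APC function is held constant within a patient.
- Autologous strength is resampled from the Table 3 pre/post CD4 + CD8 scores, with T cells drawn at the same visit as the APCs. Third-party strength is constant.
- Noise SD is 0.3 on the log scale.
- The test is the paired Wilcoxon at 0.05, with 3,000 simulated trials per setting.

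The noise, the background, the visit-matched collection and the autologous shares are assumptions of this review. The table gives the rate of a significant change when APC function has not changed.

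| Share on autologous responders | n = 9 | n = 18 |
|---|---|---|
| 0% | 0.04 | 0.05 |
| 25% | 0.11 | 0.24 |
| 50% | 0.30 | 0.70 |
| 75% | 0.66 | 0.97 |
| 100% | 0.98 | 1.00 |

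With one fixed responder source per patient, the rate returns to 0.043 (n = 9) and 0.047 (n = 18). This cures the responder effect only; step 1 is untouched.

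**The case against.** **The text allows a sound assay.** Section 11.11.7 does not say when autologous T cells are collected. Cells are frozen and stored under 11.11.2, so one banked batch per patient would fit the wording and remove the drift. Ovarian-cancer T cells and healthy-donor T cells are also planned, and vaccinating the study patient changes neither. This stands, and it makes the responder problem conditional. The healthy-donor readout is only a partial safeguard, because it does not test processing and presentation of NY-ESO-1.

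**The error rates are hypothetical.** The autologous share is not stated. The bracketed scores in Table 3 are undefined and do not always agree with the plus signs (patient 9's CD4 goes from three pluses to four, but from 1 to 4 in brackets). Table 3 reflects vaccine plus decitabine, so it cannot isolate vaccination. The Wilcoxon test in 19.4 is not tied to this assay, and 19.6 is purely descriptive. All of this stands. The presence/absence counts in step 2 do not depend on the scoring.

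**The protocol is cautious about dysfunction.** It says a missing response could reflect APC dysfunction, and 11.11.4 names Treg activity as a competing mechanism. There is no rule that labels a null result as dysfunction. This also stands.

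**A vaccine effect may not persist in cultured APCs about two weeks later.** The documents do not settle this. But the plan looks for a decitabine effect at cycle end, after 23 days without decitabine, so persistence alone is no reason to discount the other agents. The attribution problem survives.

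**Conclusion.** The attribution point holds on the text alone and needs no simulation. Changes in APC function and Treg subsets from a pre-vaccine baseline cannot be credited to decitabine when 3 or 5 vaccine doses and 4 or 8 nivolumab doses fall in the same interval.

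The responder point holds conditionally, for patients assigned autologous responders collected afresh at each visit. Its size is unknown. About 5% to 100% at n = 18 is a range over the unstated autologous share under the assumptions above, not an error rate of this trial.

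A reader might infer that the assay is bound to show a false decitabine effect, or to report APC dysfunction in every immune non-responder. The documents do not support that: collection timing is open, two unaffected responder sources are planned, and no decision rule is given. That a non-responder's autologous readout is null regardless of the APCs follows from having no responder cells; it is not a computed rate.

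The consequence is confined to a correlative, explanatory assay. The primary safety endpoint is unaffected. The change is still worth making, because it is cheap and alters what the trial can conclude.

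**What to change.** In 11.11.7:

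1. Add the pre-dose Cycle 1 Day 1 blood, already drawn, as the comparator for the post-cycle-2 and post-cycle-4 APC samples. State that it follows one vaccine dose rather than three or five, so the agents are only partly separated.
2. Attribute APC and Treg changes to decitabine plus nivolumab given with vaccine, not to decitabine. The two drugs start on the same day and this design cannot separate them.
3. Use one responder source per patient for all APC time points: HLA-suitable ovarian-cancer T cells, or a single banked autologous collection. State that a null autologous result in an immune non-responder is not evidence of APC dysfunction. Where neither source is usable, rely on the planned healthy-donor readout and its narrower meaning.

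The cost is protocol wording, batch planning of frozen cells and one extra APC culture per patient. That culture may not be possible when cell numbers are low, which 11.11.1 and 11.11.3 already foresee. Some patients will then have only the healthy-donor readout or no Cycle 1 Day 1 comparator, and the number affected should be reported.

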11.11.8 Additional Exploration of the T cell Response

Specimens will be stored for future use/analysis: The subjects enrolled at RPCI will have signed a separate consent for the taking, storage, and future research upon these samples under protocol CIC 98-05.

12 WITHDRAWAL OF SUBJECTS

Participants may remain on study and continue to receive treatment in the absence of disease progression, unacceptable toxicity or withdrawal from study, intercurrent illness that prevents further administration of treatment, participant demonstrates an inability/refusal to comply with treatment or, participant withdraws from study.

12.1 Treatment Discontinuation

Upon treatment discontinuation all end of treatment evaluations and tests will be conducted. All participants who discontinue due to an AE must be followed until the event resolves or stabilizes. Appropriate medical care should be provided until signs and symptoms have abated, stabilized, or until abnormal laboratory findings have returned to acceptable or pre-study limits. The final status of the AE will be reported in the participant's medical records and the appropriate eCRF. Patients

PROTOCOL TITLE: I 49217 - Phase 1 CDX-1401/ Poly-ICLC +Decitabine +Nivolumab in Patients with MDS or Low Blast Count AML

with dose limiting toxicities requiring drug discontinuation will be removed from the study and will not be replaced.

Reasons for treatment discontinuation should be classified as follows:

- Death
- Progressive disease
- Toxicity; treatment related or unrelated
- Investigator judgment
 - The Investigator may discontinue a participant if, in his/her judgment, it is in the best interest of the participant to do so.
- Noncompliance
- Participant voluntary withdrawal
 - A participant may withdraw from the study at any time, for any reason. If a participant discontinues treatment, an attempt should be made to obtain information regarding the reason for withdrawal.
- Sponsor Investigator's decision.

13 RISKS TO SUBJECTS

13.1 Vaccine (Anti DEC-205-NY-ESO-1 Fusion Protein (CDX-1401)/ Poly ICLC)

Expected toxicities with CDX-1401/poly ICLC include injection site reactions, including rash, erythema, pruritus, pain, induration and swelling. Additional reported treatment-related toxicities with this agent have been mild to moderate in severity, and include fatigue (24%), decreased appetite (14%), nausea (10%), arthralgia (10%), headache (10%) and pruritus (10%).

13.2 Nivolumab

In ongoing studies that combine nivolumab and HMAs in patients with myeloid malignancy (45, 46), the following adverse events have been reported:

- In 39 patients with MDS either previously untreated or relapsed after HMA failure (45):
 - 45%: constipation and maculopapular rash
 - 36%: nasal congestion
 - 27%: arthralgia, cough, stomach pain
 - 18%: diarrhea, edema, fatigue, hyperkalemia, insomnia
 - 9%: anorexia, dyspnea, GERD, hyperglycemia, hyponatremia, hypotension, mucositis, nausea, pneumonitis, weight loss

The most commonly reported \geq Grade 3 adverse events in the combination arm (n=11) were pulmonary infections (seen in 18% of patients), followed by intracranial hemorrhage, hyperglycemia, fever and elevated LFTs (in 9% each).

- In 51 patients with relapsed or refractory AML treated to date and analyzed after a total of 3 courses of therapy (46), notable toxicities reported included:

PROTOCOL TITLE: I 49217 - Phase 1 CDX-1401/ Poly-ICLC +Decitabine +Nivolumab in Patients with MDS or Low Blast Count AML

- Grade 3/4 and Grade 2 immune mediated toxicities in 7 (14%) and 6 (12%) pts.
- Pulmonary toxicity was prominent in this population with 8 episodes of pneumonitis
- Other toxicities included 2 reports of nephritis, 2 reports of transaminitis, and 1 skin rash.
- There was one death on study deemed related to grade 4 pneumonitis/epiglottitis
- Four patients were post-SCT and one had a grade 3 flare of GVHD of the skin and gut

Toxicities were reported to respond rapidly to steroids. Patients were successfully re-treated with nivolumab after resolution of toxicity. Time to onset of toxicities ranged from 4 days to 3.5 months.

Refer to **Appendix I** for reported adverse drug reactions for nivolumab monotherapy.

Note: All adverse drug reactions for nivolumab monotherapy are also adverse drug reactions for nivolumab in combination with ipilimumab and other agents. A description of adverse drug reactions nature and frequency observed with nivolumab in combination with ipilimumab can be found in the nivolumab Investigator Brochure (v16, Table 5.6.1-2)

13.2.1 Management of Immune-Related Adverse Events

Nivolumab is approved in multiple solid tumor indications as well as for Hodgkin lymphoma based on its favorable benefit/risk assessment. In hematological malignancies including multiple myeloma, nivolumab monotherapy was generally well tolerated and toxicity profile was similar to that observed in solid tumors. Nivolumab has the potential for clinically relevant immune-related AEs potentially caused by an inflammatory mechanism. These include pulmonary toxicity, hepatotoxicity, diarrhea/colitis, endocrinopathies, and nephrotoxicity.

To date, these immune-related AEs have been manageable with frequent monitoring, prompt diagnosis, and initiation of corticosteroids, dose interruption, and adequate supportive care.

Refer to **Appendix H** for algorithm guidelines for the management of immune-related adverse events.

13.3 Decitabine

Autoimmune reaction (antiplatelet antibodies, erythema nodosum), decreased hemoglobin, decreased leukocytes (total WBC), decreased neutrophils/granulocytes (ANC/AGC), decreased platelets, febrile neutropenia with or without infection, fatigue (lethargy, malaise, asthenia), alopecia, diarrhea, peritonitis, nausea, vomiting, anorexia, stomatitis /pharyngitis (oral/pharyngeal, mucositis), increase bilirubin, increased SGOT (AST) (serum glutamic oxaloacetic transaminase), increased SGPT (ALT) (serum glutamic pyruvic transaminase), depressed level of consciousness, abdominal pain or cramping.

The following have been reported on decitabine trials with the relationship to decitabine still undetermined: Allergy, GVHD, atrial fibrillation, thrombosis, phlebitis, cardiac ischemia, cardiac arrest (one case), face edema, hypotension, cardiac failure/arrest (MI), congestive heart failure, veno-occlusive disease, ascites, cardiac decompensation, fever, chills, drug fever, weight loss, skin rash, itching, taste disturbance, constipation, cholecystitis, perianal abscess, ileus, hematuria, liver failure, increased alkaline phosphatase, reactivation of herpes simplex, hyponatremia, neuropathy,

PROTOCOL TITLE: I 49217 - Phase 1 CDX-1401/ Poly-ICLC +Decitabine +Nivolumab in
Patients with MDS or Low Blast Count AML

depression, dizziness, headache, lightheadedness, restlessness, sleep disorder, seizures, hemiparesis, somnolence, myalgia, bone pain, dyspnea, hiccups, pulmonary edema, ARDS, cough, increased creatinine, dysuria, renal failure, bone marrow aplasia, infectious complication (including sepsis, infection cellulites, pneumonia), GI bleed, cerebral hemorrhage, cerebral ischemia, lung hemorrhage, differentiation syndrome, infection with normal absolute neutrophil count.

